During the implementation phase of RP, the study team will meet weekly, or more frequently if needed, with site's clinical staff and other key stakeholders to provide coaching support and monitoring during the initial implementation of the intervention. The study team or lead implementation team will meet routinely to review the implementation process and identify modifiable barriers or facilitators to facilitate RP implementation. The study team will reduce coaching support as each site takes lead in implementing RP and at that point the site will shift into the maintenance phase. During the maintenance phase, all sites randomized to RP will meet routinely in a collaborative coaching session and the study team will reduce support further and act in a monitoring role.

After each stepped wedge, the study team with expertise in implementation will meet to review identified barriers and facilitators to implementing the RP intervention and modify or adapt the RP IF package accordingly. Barriers and facilitators mapped across the CFIR framework will be captured using various qualitative data including structured notes from Site Mapping meetings and coaching sessions, internal implementation team meeting notes, and staff structured interviews at the end of each stepped wedge. Review of other implementation-level data at the end of the study will inform final adaptations or modifications to the RP IF package. This IF package will form the basis of technical assistance and support widespread dissemination of rapid XR-NTX initiation.

The Standard Procedure follows treatment as usual for induction onto XR-NTX and it is expected that site-level processes are already established for implementing SP (preconditions to be selected for study participation). Given these preconditions, SP sites do not require systematic implementation facilitation support. A brief overview and training of SP (primarily based on the XR-NTX prescribing information) will be provided at the start of the trial. Throughout the trial, the study team will meet with sites implementing SP for monitoring and engaging treatment teams in study participation.

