2.2 Study Design and Procedures

2.2.1 Study Design

This is a six-center, stepped-wedge, cluster randomized trial comparing effectiveness and safety of Rapid (5-7 days) versus Standard (13 days) XR-NTX induction procedure (RP vs. SP). The study will proceed in five steps, with each step lasting 14 weeks, for the total of 70 weeks of the study (Table 2). A total of 450 participants (15 per site per step) eligible for and seeking treatment for opioid disorder with XR-NTX and consenting to research assessments during their course of XR-NTX treatment are planned to be enrolled in the study. Enrolled participants will receive the naltrexone initiation regimen being offered at the site at the time of admission, either SP or RP depending on the random assignment as per study design. At the beginning of each step a randomly selected site will begin implementing RP and will continue to offer it for the remainder of the trial, according to the optimized stepped-wedge study design (Thompson et al., 2017). Note the first randomized site will offer only RP whereas the last remaining site will offer only SP for the entire duration of the trial. After sites transition to RP, this will be the only regimen available for patients interested in participating in the research study (i.e., SP will no longer be offered as a part of the study). Before each stepped wedge of the study, an 8-week pre-implementation or preparation phase will occur for each site randomized to RP. During the implementation phase of RP, the implementation team will meet routinely to review the implementation process and identify modifiable barriers or facilitators to facilitate RP implementation. After each stepped wedge, the study team with expertise in implementation will meet to review identified barriers and facilitators to implementing the RP intervention and modify or adapt the RP Implement Facilitation package accordingly. Site level and provider/staff level surveys will be completed before and after implementation of RP.

Table 2: Schematic of study design with six study sites and five steps, each lasting 14 weeks

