8.2 Analysis of the Primary Outcome Measure

A summary of the number of participants who receive their first injection will be presented by site, by step and by induction procedure. The main analyses for the primary outcome will use the ITT population. As is standard for the analysis of stepped-wedge designs (Barker et al., 2016; Hussey and Hughes, 2007), the primary outcome analysis for non-inferiority will be performed using a generalized linear mixed-effects model with a logistic link. The log odds of a participant receiving the first XR-NTX injection (yes/no) will be modeled as a function of which induction procedure (RP vs SP), step 1 through 5 (to control for secular trends), and a random effect for site to control for nesting of participants within site. The null hypothesis of inferiority of RP to SP will be rejected if the lower 95% confidence limit of the odds ratio of success [odds(RP)/odds(SP)] exceeds 0.67. If null hypothesis of inferiority of RP to SP is rejected, then superiority of RP will be tested. If the 95% confidence interval for the odds ratio is above 0.67 and is also above 1, then there will be evidence of superiority and it is acceptable to calculate the p-value (CPMP, 2001). The covariance structure compound symmetry (CS, correlations over time are constant) will be used for the observations from a particular site. Other correlation structures will be examined (Hemming et al., 2017). The best model will be selected based on the lowest Bayesian Information Criterion (BIC). The Satterthwaite method to adjust for denominator degrees of freedom for tests of the fixed effects will be used.

Logistic model will be used:

$$\begin{aligned} \text{logit}(p_{ijs}) &= J_{js} * \delta + \theta_s + \alpha_j \\ \alpha_j &\sim N(0, \tau^2) \end{aligned}$$

Alternative logistic model with autoregressive lag-1(AR(1)) correlation structure:

$$\begin{aligned} \text{logit}(p_{ijs}) &= J_{js} * \delta + \theta_s + \alpha_{js} \\ \alpha_{js} &\sim N(0, \tau^2) \\ \text{Cov}(\alpha_{js}, \alpha_{jt}) &= \tau^2 \rho^{|t-s|} \end{aligned}$$

where:

- j indexes the site
- s indexes the step
- i indexes the individual within site j at time s
- θ_s is the fixed effect of time

- α_j is the random site effect
- p_{ijs} is the probability of success for individual i within site j at time s
- J_{js} is the treatment indicator for site j at time s
- δ is the treatment effect
- t and s index two different steps (in AR(1) model)

SAS code example:

```

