proc glimmix data = primout method = quad IC = PQ;  
  class site trt (ref='SP') step (ref='1');  
  model success (event='1') = trt step / dist = binary link = logit solution oddsratio;  
  random intercept / subject = site;  
run;
```

SAS code example AR(1):

```
proc glimmix data = primout method = quad IC=PQ;  
  class site trt(ref='SP') step (ref='1');  
  model success (event='1')= trt step / dist = binary link = logit solution oddsratio;  
  random step / subject=site type=ar(1);  
run;
```

where:

- success - is the XR-NTX injection status (Yes=1 or No=0)
- trt - is the variable that defines the induction procedure (RP or SP)
- step - is 1 through 5
- site - is the site code for the 6 sites.

The Number Needed to Treat (NNT) will be calculated as the inverse of the absolute difference in rates of success i.e., $1 / (\text{rate of success in RP} - \text{rate of success in SP})$.

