Under the above assumptions, the null and alternative hypotheses can be stated as follows: In terms of proportions (p):

Null (inferiority of RP to SP): $p(RP) - p(SP) \leq -0.10$

Alternative (non-inferiority of RP to SP under which power was calculated): $p(RP) - p(SP) > 0.15$

In terms of odds ratios (OR):

Null (inferiority of RP to SP): $OR [odds(RP)/odds(SP)] \leq 0.67$

Alternative (non-inferiority of RP to SP under which power was calculated): $OR [odds(RP)/odds(SP)] > 1.91$

Intraclass Correlation Coefficient: The ICC estimate is based on a logistic regression of induction success/failure in CTN-0051 on treatment arm, with a random site effect whose variance is allowed to depend on arm. It is assumed that any extra covariates added to the model will improve

analysis accuracy, implying that current power estimates are conservative. The estimated site standard deviation in the XR-NTX arm from the regression model using data from CTN-0051 is 0.86, leading to an estimated ICC in the SP arm of 0.14 under the generalized mixed model. The ICC represents the correlation between two individuals chosen randomly without replacement from the XR-NTX arm of CTN-0051, given that they come from the same site.

In summary, the assumptions used for the power calculations for this non-inferiority optimized stepped-wedge cluster randomized trial are as follows:

- The projected number of clusters is 6 (sites), that will enroll participants across 5 periods of time, each period 14 weeks long.
- The projected total number of participants enrolled is 450, with 15 participants enrolled per cluster per time period (equal allocation to sites per time period).
- The outcome of interest is a binomial outcome (the participant received or did not receive the first XR-NTX injection).
- The probability of success in the SP arm is 0.55.
- The probability of success in the RP arm is 0.70 (i.e., an effect size of 0.15).
- The margin of non-inferiority is 10%, which corresponds to an odds ratio of 0.67 (based on proportion of success in RP = 0.45 and proportion of successes in SP = 0.55). Refer to Figure 5 for the relationship between non-inferiority margin as a difference in proportions versus non-inferiority margin as an odds ratio.
- Observations are equally correlated within cluster, regardless of time or induction method with a site standard deviation of 0.86. The corresponding ICC in the SP arm based on a logistic regression with random effects is 0.14.

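### The primary odds ratio assumes one constant RP effect and mainly reflects each site's first two RP steps; SAP 8.3 item 4 should examine time since switch rather than study month alone

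*SAP*

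**What the plan says.** SAP 8.2 fits a mixed logistic model in which the log odds of receiving the first injection "will be modeled as a function of which induction procedure (RP vs SP), step 1 through 5 (to control for secular trends"), with a random effect for site. The SAS statement is "model success (event='1') = trt step / dist = binary link = logit solution oddsratio". In the model key, "δ is the treatment effect": one parameter covers every RP site-step. "The covariance structure compound symmetry (CS, correlations over time are constant) will be used for the observations from a particular site"; other structures, including a written-out AR(1) model, may replace it on lowest BIC. Neither version has a term for time since a site switched. Non-inferiority is declared if the lower 95% confidence limit of this odds ratio exceeds 0.67.

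On the layout, SAP 12.0 states "The projected number of clusters is 6 (sites), that will enroll participants across 5 periods of time", with 15 participants per site per step. SAP 2.2.1 adds that "the first randomized site will offer only RP whereas the last remaining site will offer only SP". One further site switches at each step.

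On delivery, Protocol 6.2 provides coaching at least weekly during initial RP implementation. Then "The study team will reduce coaching support as each site takes lead in implementing RP", with a further reduction in the maintenance phase. After each step the team will "modify or adapt the RP Implement Facilitation package accordingly" (SAP 2.2.1).

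SAP 8.3 item 4 plans a supportive test of procedure by study month, on the reasoning that a significant result would point to a different impact once there has been more experience.

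**The concern.** A single δ is a fair summary if RP's effect does not depend on how long a site has used it. The documents leave that open: support changes with time on RP, the package is revised as the trial proceeds, and item 4 looks for a change with experience.

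If the effect does vary with time since switch, a stepped-wedge model with one treatment term and step effects does not return the average of the RP effects over participants. It returns a weighted sum whose weights are set by the layout and the covariance. Those weights decide which part of each site's RP experience the 0.67 rule judges. If they sit mostly on the first steps, the conclusion describes newly introduced, intensively coached RP more than RP over the whole trial. That matters for a study meant to support wide adoption.

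**Working it through.** **Inputs (SAP 12.0 and 2.2.1).** 6 sites, 5 steps, 15 per cell; success 0.55 (SP) and 0.70 (RP); site SD 0.86 on the logit scale; margin 0.67. The RP cells in a site's 1st to 5th RP step number 5, 4, 3, 2 and 1, 15 in all. The participant shares are therefore 5/15, 4/15, 3/15, 2/15 and 1/15.

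**The plan's own figure.** Data were simulated from a logistic-normal model with SD 0.86 and marginal rates 0.55 and 0.70 (conditional odds ratio 2.11). The 8.2 model was fitted by quadrature, and non-inferiority was declared if the Wald lower 95% limit exceeded 0.67. Power was 0.886 in 6,000 runs, against the stated 0.887.

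**Weights.** On cell logits, the generalised least squares estimate is δ̂ = the treatment element of (X'V⁻¹X)⁻¹X'V⁻¹y. X holds the RP indicator and five step effects. For each site V = τ²11' + diag(1/(15p(1-p))). With τ² = 0.86² = 0.74 and p = 0.625 (midway between 0.55 and 0.70), the cell variance is 1/(15 × 0.625 × 0.375) = 0.284. Summing the weights on RP cells by step since switch gives:

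| RP step since switch | 1 | 2 | 3 | 4 | 5 |
|---|---|---|---|---|---|
| Participant share | 0.33 | 0.27 | 0.20 | 0.13 | 0.07 |
| Compound symmetry | 0.79 | 0.36 | 0.06 | -0.09 | -0.12 |
| AR(1), ρ = 0.9 | 0.84 | 0.26 | 0.02 | -0.06 | -0.06 |
| AR(1), ρ = 0.7 | 0.79 | 0.19 | 0.04 | -0.01 | -0.02 |
| AR(1), ρ = 0.5 | 0.68 | 0.20 | 0.09 | 0.03 | 0.01 |

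With p = 0.55 in SP cells and 0.70 in RP cells, the compound-symmetry row is 0.75, 0.35, 0.08, -0.08, -0.11. With site variance from 0.05 to 10 (p = 0.625), the first weight runs from 0.54 to 0.85 and the fifth from -0.02 to -0.14. Under compound symmetry the negative cells are site 1 at steps 4 and 5 and site 2 at step 5.

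**Hand check of one scenario.** Let RP's odds ratio be 1.0 in a site's first two RP steps and 0.35 afterwards (ln 0.35 = -1.050).
- Participant-weighted: (0.20 + 0.13 + 0.07) × (-1.050) = -0.42, an odds ratio of 0.66, below the margin.
- Model-weighted, with the later weights to three decimals: (0.064 - 0.094 - 0.115) × (-1.050) = +0.152, an odds ratio of about 1.16.

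**Simulation of the full model (compound symmetry, SD 0.86).** The shapes of change are assumptions; the documents give none. There were 4,000 runs for the constant case and 2,000 for each other case.

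| RP odds ratio by step since switch | Participant-weighted OR | Mean estimate | Non-inferiority declared |
|---|---|---|---|
| 0.67 throughout | 0.67 | 0.66 | 4.0% |
| 1.0, then 0.5 | 0.63 | 0.84 | 12% |
| 1.0, 0.67, 0.5, 0.4, 0.33 | 0.64 | 0.99 | 23% |
| 1.0, 1.0, then 0.35 | 0.66 | 1.13 | 34% |
| 0.33, 0.4, 0.5, 0.67, 1.0 | 0.45 | 0.30 | 0% |

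The last row shows the direction of the error under improvement: the estimate falls below the participant-weighted value.

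**What item 4 can detect.** A linear procedure-by-calendar-step term has approximate two-sided 5% power of 27% for the decline from 1.0 to 0.33, and 37% for the fall to 0.35. A linear term in time since switch has about 48% and 64%.

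**The case against.** The strongest reply is that the plan already looks for this. Item 4 tests for a changing effect, and the shell for SAP Table 32 reports the percentage inducted in every site-by-step cell, so a fall after a site's first RP steps would be visible. A reader might infer that no planned analysis bears on the problem; the documents do not support that. But calendar month is not time on RP: a site switching at step 5 contributes late-month RP data with no prior RP experience. Item 4 also yields a test rather than an odds ratio by time on RP, and Table 32 gives raw rates with no model-based contrast.

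A reader might also infer that the model generally rewards an RP that deteriorates, because late steps carry negative weight. That goes too far. Only 3 of the 15 RP cells are negative, summed by calendar step all RP weights are positive, and under the AR(1) alternative the negative weights shrink to about zero at ρ = 0.7. What survives the covariance choice is the dominance of early steps.

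Nor do the documents say that coaching is withdrawn or that RP will get worse. Support is reduced, while collaborative sessions continue and individual coaching remains available as needed (Protocol 6.2.1). Revising the package after each step could equally bring improvement.

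Finally, SAP 8.2 does not say over which steps a varying RP effect should be averaged. The three declining scenarios were therefore judged on the participant-weighted average, which lies below 0.67 in each.

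**Conclusion.** The point holds as a limit on what the primary odds ratio describes. Under the planned layout and site SD, about 1.15 of the total weight of 1 falls on each site's first two RP steps (0.79 + 0.36), which hold 60% of RP participants (9 of 15 cells). Under AR(1) with ρ from 0.5 to 0.9, those two steps still carry 0.88 to 1.10.

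If RP's effect is constant, the primary analysis does what it claims. If the effect falls with time on RP, the chance of declaring non-inferiority with a participant-weighted odds ratio below 0.67 was 12% to 34% in the assumed scenarios, against 4% at a constant 0.67. These figures assume equal cells of 15, SD 0.86, compound symmetry and declines of the sizes shown. They do not show that a decline is likely, and they give no reason to replace the primary rule. This is a worthwhile, inexpensive improvement to an existing supportive analysis.

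**What to change.** In SAP 8.3 item 4, replace study month, or supplement it, with time since the site's switch to RP. Refit the 8.2 model with RP split into a site's first two RP steps and its later ones. Report both odds ratios with 95% confidence intervals, and their average over the 15 RP site-steps (weights 9/15 and 6/15 on the log scale), labelled supportive. Leave the primary model and the 0.67 rule unchanged.

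Do not add a rule that restricts the conclusion when the later-step interval fails to clear 0.67. With a standard error of about 0.54 and a truly constant odds ratio of 1.91, (ln 1.91 - ln 0.67)/0.54 = 1.94, so the later-step lower limit would clear 0.67 only about half the time even though RP never worsened.

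The cost is one more model and one table. Approximate standard errors on the log odds scale are 0.34 (early), 0.54 (later) and 0.39 (average), against 0.33 for the primary estimate. The later-step estimate rests on 6 cells from three sites and should be read as descriptive only.

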16.3 Statistical Methods for Primary and Secondary Outcomes

16.3.1 Primary Outcome Analysis

As is standard for the analysis of stepped-wedge designs (Barker *et al.*, 2016) the primary outcome analysis for non-inferiority will be performed using a generalized linear mixed effects model with a logistic link, similar to the model used for the power calculations. The log odds of a participant receiving the first XR-NTX injection (yes/no) will be modeled as a function of which treatment they received (RP vs SP), which study month it is (to control for secular trends), and a random effect for site to control for nesting of participants within site. We will reject the null of inferiority of RP to

SP if the lower 95% confidence limit of the odds ratio of success [odds(RP)/odds(SP)] exceeds 0.67. Supplemental analyses related to the primary objective will test for a treatment*study month interaction, which, if significant, would indicate differential impact of treatment after a longer period of experience. Sensitivity analyses of the primary outcome may be performed to account for different correlation structures.

16.3.2 Secondary Outcome Analysis:

Secondary outcomes will include receiving 2nd and 3rd monthly injections of naltrexone, and opioid withdrawal symptoms and adverse events during and in the month after XR-NTX initiation. These outcomes will be modeled using similar mixed effects logistics regression methods as above. Note that the analysis of secondary outcomes before first XR-NTX injection will be performed using all enrolled participants using an intent-to-treat population (ITT) whereas the analyses of secondary outcomes after receipt of first XR-NTX injection will be performed for all enrolled participants as well as for a subset of the ITT population i.e., all enrolled participants who successfully received the scheduled XR-NTX injections (inducted population).

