11.0 SIGNIFICANCE TESTING AND MULTIPLICITY

There is only one primary outcome and therefore no adjustments for multiple testing are planned for the primary outcome analysis. The primary outcome and the supportive analysis for the primary outcome will use a one-sided test with 2.5% type I error rate. A similar error rate will be used if the test of superiority is performed. A restricted list of secondary outcomes was chosen a priori, and, in addition, the key secondary outcomes are not intended to be confirmatory in nature. Therefore, no multiple adjustments are planned for analyzing multiple secondary outcome measures. When multiple tests are conducted, the chance of finding a significant difference in one of the tests, when in fact no difference exists, is greater than the stated type I error rate. The investigators are aware of the issues associated with multiple testing and will interpret results with caution. The secondary outcomes will use a two-sided test with 5% type I error rate.

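### SAP 8.2 lets BIC choose the confirmatory model from outcome data, and SAP 12.0 treats a 10-point margin and a site-conditional odds ratio of 0.67 as one null, so the 2.5% error rate is only nominal

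*SAP*

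**What the plan says.** **Model.** SAP 8.2 specifies a logistic mixed model with treatment, step and a random site effect. On the correlation structure it says "The covariance structure compound symmetry (CS, correlations over time are constant) will be used for the observations from a particular site". It then says that other structures will be examined, and: "The best model will be selected based on the lowest Bayesian Information Criterion (BIC"). Only an AR(1) alternative is written out. On inference it says "The Satterthwaite method to adjust for denominator degrees of freedom for tests of the fixed effects will be used"; the code example carries no degrees-of-freedom option.

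**Protocol.** Section 16.3.1 describes the random-site model and adds only "Sensitivity analyses of the primary outcome may be performed to account for different correlation structures".

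**Decision rule.** SAP 8.2: "The null hypothesis of inferiority of RP to SP will be rejected if the lower 95% confidence limit of the odds ratio of success" lies above 0.67. SAP 11.0: "The primary outcome and the supportive analysis for the primary outcome will use a one-sided test with 2.5% type I error rate".

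**Margin and planning values.** SAP 12.0: "The margin of non-inferiority is 10%, which corresponds to an odds ratio of 0.67", taken from rates of 0.45 and 0.55. The null is written twice, as a difference of −0.10 or worse and as an odds ratio of 0.67 or less. It also says "Observations are equally correlated within cluster, regardless of time or induction method with a site standard deviation of 0.86". Section 12.0 simulates power and reports no type I error.

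**The concern.** Three things bear on the trial's only confirmatory test.

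- **The primary model is not fixed.** Compound symmetry is named and then made subject to a BIC comparison over candidates that are not all listed. BIC is computed from the outcome data, so the confidence limit that decides the trial comes from a model chosen after those data are seen. The protocol does not do this.
- **The margin has two meanings.** The treatment coefficient in a random-site logistic model is a log odds ratio for a given site. Rates of 0.45 and 0.55 averaged over sites do not give the same odds ratio when sites differ.
- **The actual error rate is not reported.** With six sites, maximum likelihood tends to underestimate the site SD, so standard errors come out too small. A reader may expect the Satterthwaite step to deal with this.

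At stake is how often a rapid procedure lying exactly on the limit would be declared non-inferior, and whether 2.5% can be quoted for that.

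**Working it through.** **Inputs (SAP 12.0 unless noted).** 6 sites, 5 steps, 15 participants per site-step (450 in total); one site crosses over per step, with one site always RP and one always SP; site SD 0.86 on the logit scale; SP rate 0.55, RP rate 0.70 for power; limit 0.67; lower 95% limit rule (SAP 8.2). Assumed: normal site effects, equal cells, no secular trend, random-intercept model correct. Site SDs other than 0.86 are assumptions.

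**1. Reproduce the plan's own figures.**
- Margin: (0.45/0.55) / (0.55/0.45) = 0.669.
- Power with 0.55 and 0.70 as marginal rates (conditional OR 2.11): 0.884–0.895 in one simulation, and 0.886–0.888 (t on 439 df, normal) in a second, separately programmed one. The SAP states 0.887.
- Power with the SAP's OR of 1.91 as the conditional OR: 0.831–0.845 and 0.830. This does not match.
- ICC: 0.138 on the probability scale, against the stated 0.14. The logit-scale value would be 0.86² / (0.86² + 3.29) = 0.18.

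The planning figures therefore come from marginal rates.

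**2. Put the two nulls on one scale.** A marginal rate is the average of expit(b + site effect) over site effects with SD 0.86.
- Marginal 0.55 and 0.45 need b = +0.233 and −0.233, so the conditional OR is exp(−0.466) = 0.628.
- Conditional OR 0.67 moves b to 0.233 − 0.400 = −0.168, a marginal rate of about 0.464. The difference is 0.464 − 0.55 = −0.086.

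**3. Error at the limit, by hand.** In simulation at conditional OR 0.67 the fitted site SD averages about 0.72–0.73 against 0.86. The mean model SE of the log OR is 0.337–0.347, and its empirical SD is 0.368.
- Effective cut-off: 1.96 × 0.347/0.368 = 1.848, tail 3.2%; 1.96 × 0.337/0.368 = 1.795, tail 3.6%.
- Marginal null: the truth lies (0.466 − 0.400)/0.368 = 0.18 further from the limit, so the cut-offs become about 2.03 and 1.97, tails 2.1% and 2.4%.

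**4. Error at the limit, by simulation.**

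| Null | Site SD | Simulation 1 | Simulation 2 |
|---|---|---|---|
| Conditional OR 0.67 | 0.86 | 3.2–3.7% | 3.2–3.5% |
| | 0.5 | 3.8–4.4% | 4.1–4.4% |
| | 1.2 | 3.0–3.3% | 2.8–3.1% |
| Marginal 0.45 vs 0.55 | 0.86 | 1.8–2.1% | 2.1–2.4% |
| | 0.5 | 3.2–3.7% | 3.6–3.7% |
| | 1.2 | 1.4–1.6% | 1.3–1.5% |

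Simulation 1 uses per-dataset Satterthwaite df; its range runs from the full-information SE to the SE with site variance treated as known (15,000–20,000 runs per row). With a fixed cut-off of 1.96 its marginal figure at SD 0.86 is 2.2–2.5%. Simulation 2 runs from a normal to a Satterthwaite reference (20,000 runs at SD 0.86, 10,000 elsewhere). Monte Carlo SE is about 0.1–0.2 points. A smaller and cruder run gave about 3.5–4.5% (conditional) and 2.6% (marginal) at SD 0.86.

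**5. Why Satterthwaite does not help.** Median df at SD 0.86 are 214 and 224 in the two simulations. A t distribution with 200 df has a 97.5% point of about 1.97, so the cut-off hardly moves from 1.96.

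**6. BIC.** No arithmetic applies. The SAP's selection sentence and the protocol's sensitivity-analysis sentence give other structures different roles. The effect of BIC selection on error was not simulated.

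**The case against.** The strongest reply is that the SAP's numbers lean to the marginal reading. The hypothesis is about a proportion of participants, the margin is stated as 10 points, the number needed to treat uses a difference in rates, and both the ICC and the power reproduce only with marginal rates. On that reading the error at the planning SD is near or below 2.5%. This stands, and it rules out a flat statement that the 2.5% is not met. It does not settle the matter: the SAP never labels the odds ratio, its rule is applied to the site-conditional one, and at an assumed SD of 0.5 the marginal reading also exceeds 2.5%.

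Second, the excess is modest: 3.2–3.7% is 0.7–1.2 points above nominal, some departure is expected of a Wald limit with six clusters, and the top of the range treats the site variance as known. All of that is fair.

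Third, the BIC rule is pre-specified and selects on fit, not on the treatment result. The protocol is also not a clean compound-symmetry benchmark: 16.3.1 promises a model similar to the power model, and the protocol's power code lets the site variance differ by treatment, which the SAP drops. These points soften the contrast. They do not close the candidate list, or reconcile a named structure with a later selection step.

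**Conclusion.** Two points stand on the text and simple algebra. SAP 8.2 leaves the confirmatory model to an outcome-based choice that the protocol does not provide for. SAP 12.0 equates two nulls that differ under its own model: −8.6 against −10 points, or conditional odds ratios of 0.67 against about 0.63, at site SD 0.86.

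The error-rate point is conditional. It is about 3.2–3.7% if 0.67 is the conditional odds ratio, and near or below nominal at SD 0.86 if marginal 0.45 vs 0.55 is meant. It moves with the unknown site SD on either reading. These figures rest on equal cells, no secular trend and a correct random-intercept model.

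Three stronger readings are tempting and unsupported:
- That the trial simply breaches its 2.5%. The reading that reproduces the power does not show this at the planning SD.
- That BIC selection causes the excess. The excess arises with compound symmetry fixed, and selection was not simulated.
- That the threshold should be loosened to about 0.63. SAP 8.3 already refers to enrolled participants, so that would change the margin after enrolment began, and it would bring back the same small-sample excess at the new limit.

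This should be fixed; it does not invalidate the design.

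**What to change.** Before database lock:

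1. In SAP 8.2, name the random-intercept (compound symmetry) model as the only primary model. Delete the BIC selection. Report AR(1) and any other structures as sensitivity analyses, in line with protocol 16.3.1.
2. Keep the threshold at 0.67. State that it applies to the site-conditional model odds ratio, and correct the statement in SAP 12.0 that it corresponds to exactly 10 points.
3. Report in SAP 12.0 the simulated type I error and power of that exact procedure, with the degrees-of-freedom method the same in text and code, over a range of site SDs and under both nulls. Describe 2.5% as nominal.
4. Optionally, report a small-sample reference alongside, for example t on 30 cells − 5 steps − 1 treatment − 5 site parameters = 19 df (cut-off 2.093). At conditional OR 0.67 the first simulation gives 2.5–2.9% at SD 0.86, but 2.8–3.4% at 0.7 and 3.4–3.9% at 0.5, so it does not guarantee 2.5%. Power at marginal 0.55 vs 0.70 would be 0.857–0.871, against the stated 0.887.

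The cost is SAP wording, a re-run of the simulation and a slightly less favourable stated error rate. Design and data collection do not change.
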